### **4.2.10 Secondary Endpoint: Change in circulating GDF15 serum levels (Applicable for Substudy 1: Part A and Part B only)**

#### **4.2.10.1 Definition and Derivations**

Changes in free GDF15 serum levels is defined as change in GDF15 serum levels from pre-treatment (baseline) to each post baseline timepoint on the PD population.

#### **4.2.10.2 Primary Analysis of Secondary Endpoint**

The change in circulating free GDF15 serum levels from pre-treatment (baseline) to each post baseline timepoint, will be summarised using descriptive statistics. Standard summary statistics n, mean, St. Dev, median, minimum, and maximum will be presented. Summary of absolute values and percent change from baseline will be produced by cohort by visit.

Listing of individual values is provided.

Boxplot may be produced to represent the evolution of GDF15 over time. If a group has  $\leq 10$  patients, line plot will be produced instead of boxplot.

#### **4.2.11 Secondary Endpoint: Change in CD8 tumour infiltration by IHC using baseline and on treatment samples (Applicable for Substudy 1: Part A and B only)**

##### **4.2.11.1 Definition and Derivations**

Changes in CD8 tumour infiltration by IHC are defined as change in CD8 tumour infiltration by IHC from pre-treatment (baseline) from on treatment fresh biopsies (C2D8 +/- 5 days) on the PD population.

Tissue obtained as part of mandatory paired biopsies obtained before and during treatment (Screening [Day -28 to -1], C2D1 and C2D8) will be assessed for CD8+ T cell tumour infiltration.

##### **4.2.11.2 Primary Analysis of Secondary Endpoint**

The change in CD8 tumour infiltration measured by IHC will be summarised using descriptive statistics, standard summary statistics n, mean, St. Dev, median, minimum, and maximum will be presented.

Summary of absolute values and percent change from baseline will be produced.

Listing of individual values is provided.

#### **4.2.12 Pharmacokinetics**

This section covers details related to PK endpoints and analyses.

The (PK) parameters of the concentration data for AZD8853 and its metabolites (if metabolite[s] are defined and their concentrations are available) are derived using non-compartmental methods in Phoenix® WinNonlin® Version 8.1 or higher (Certara) by Clinical Pharmacology and Marketed Products at AstraZeneca

#### **Plasma PK Parameters**

PK analysis is, where data allow, carried out using actual elapsed times determined from the PK sampling and dosing times recorded in the database. If actual elapsed times are missing, nominal times may be used at the discretion of the PK Scientist with approval from the AZ Clinical Pharmacology Scientist (CPS). Nominal sampling times may be used for any agreed interim PK parameter calculations.

For each PK sampling period, plasma concentrations that are non-quantifiable (NQ) from the time of pre-dose sampling ( $t=0$ ) up to the time of the first quantifiable concentration is set to a value of zero. After this time point, NQ plasma concentrations are set to missing for all concentration profiles. Where 2 or more consecutive concentrations are NQ at the end of a

profile, the profile is deemed to have terminated and therefore any further quantifiable concentrations are set to missing for the calculation of the PK parameters unless it is considered to be a true characteristic of the profile of the drug.

If an entire concentration-time profile is NQ, the profile is excluded from the PK analysis.

Cmax, Cmin, tmax, tlag and tlast are taken directly from the concentration-time profiles.

Refer to Appendix B (Section [7.2](#)) for the calculation of PK parameters including  $\lambda_z$ , Area under the curve (AUCs), Clearance (CL), Accumulation ratio (Rac), Temporal Change Parameter (TCP), and so on.

For each analyte, plasma concentrations for each scheduled time-point are summarised by Study Part, PK Day/Visit and Treatment dose level using appropriate descriptive statistics. Similar data (e.g., single dose or multiple doses for the same dosing regimen) from different Study Parts or PK Days/Visits may also be summarised together. Individual concentrations with time deviations of greater than  $\pm 10\%$  from the protocol scheduled time, are used in the PK analysis but are flagged for exclusion from the summary tables and corresponding figures.

The following descriptive statistics are presented for plasma concentrations:

- n
- n below Lower limit of quantification (LLOQ)
- geometric mean (gmean)
- geometric coefficient of variance (%) (gCV)
- arithmetic mean (mean)
- arithmetic standard deviation (Std Dev)
- median
- minimum (min)
- maximum (max)
- 

The gmean is calculated as:

$$\exp(\mu)$$

where  $\mu$  is the mean of the data on the natural log scale.

The gCV is calculated as:

$$100 \times \sqrt{[\exp(\sigma) - 1]}$$

where  $\sigma$  is the Std Dev of the data on the natural log scale.

Where required for plots: The gSD is calculated as:

$$\exp(\sigma)$$

where  $\sigma$  is the Std Dev of the data on the natural log scale.

The gmean  $\pm$  gSD (gmean-gSD and gmean+gSD) are calculated as:

$$\exp[\mu \pm \sigma]$$

Protocol scheduled times are used to present the PK concentration summary tables and corresponding gmean concentration-time figures.

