### **Handling of Non-Quantifiable Concentrations**

Individual concentrations below the LLOQ of the bioanalytical assay are reported as NQ in the listings with the LLOQ defined in the footnotes of the relevant TFLs. Individual plasma concentrations that are Not Reportable are reported as NR and those that are missing are reported as NS (No Sample) in the listings. Plasma concentrations that are NQ, NR or NS are handled as follows for the provision of descriptive statistics:

- Any values reported as NR or NS are excluded from the summary tables and corresponding figures.
- At a time point where less than or equal to 50% of the concentration values are NQ, all NQ values are set to the LLOQ, and all descriptive statistics are calculated accordingly.
- At a time point where more than 50% (but not all) of the values are NQ, the gmean and gCV% are set to Not calculable (NC). The maximum value is reported from the individual data, and the minimum and median are set to NQ.
- If all concentrations are NQ at a time point, no descriptive statistics are calculated for that time point. The gmean, minimum, median and maximum are reported as NQ and the gCV% as NC.
- The number of values below LLOQ ( $n < \text{LLOQ}$ ) are reported for each time point together with the total number of collected values ( $n$ ).

Three observations  $>$  LLOQ are required as a minimum for a plasma concentration or PK parameter (e.g. Cmax, Cmin, Clast) to be summarised. Two observations  $>$  LLOQ are presented as minimum and maximum with the other summary statistics as NC.

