### **PK parameter descriptive statistics**

All primary and secondary PK parameters are summarised for each analyte by Study Part, PK Day/Visit and Treatment dose using appropriate descriptive statistics. Similar parameter data (e.g., single dose or multiple doses for the same dosing regimen) from different Study Parts or PK Days/Visits may also be summarised together.

The descriptive statistics for PK parameters are presented as follows:

- Cmax, Cmin, Clast, AUC(0-t), AUCinf, AUClτ, AUClast: present n, gmean, arithmetic mean of non log-transformed data (mean), arithmetic standard deviation (Std Dev), gCV(%), median, min and max.
- $t^{1/\lambda z}$ , CL, Vss, MRT, : present n, arithmetic mean of non log-transformed data (mean), arithmetic standard deviation (Std Dev), median, min and max.
- Cmax/D, AUCinf/D, AUC(0-t)/D, AUClτ/D, AUClast/D,  $\lambda z$ , and all parameter ratios (e.g Rac, TCP, peak:trough ratio and fed to fasted ratios): present n, gmean, gCV(%), mean, Std Dev, median, min and max.
- tmax, tlag, and tlast: present n, median, min and max.
- Diagnostic parameters (e.g. t upper, t lower, n obs, Rsq adj and AUCextr): present n, arithmetic mean, Std Dev, gmean, gCV%, median, min and max.

Three values are required as a minimum for PK parameters to be summarised. Two values are presented as a min and max with the other summary statistics as NC.

If one or more values for a given parameter is zero, then no geometric statistics are calculated for that parameter and the results for geometric statistics are set to NA (Not Applicable).

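### The SAP's geometric CV formula uses exp(σ) where σ is the log-scale SD; it should use exp(σ²), so the reported gCV(%) is wrong unless σ is 0 or 1

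*SAP*

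**What the plan says.** Under Plasma PK Parameters in SAP section 4.2.12, the geometric mean is exp(μ), where μ "is the mean of the data on the natural log scale". The geometric CV in percent is then "100 \times \sqrt{[\exp(\sigma) - 1" (the closing bracket is cut from the quote), and the line below says that σ "is the Std Dev of the data on the natural log scale".

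The same symbol is used straight afterwards. "Where required for plots: The gSD is calculated as" introduces exp(σ), with the same definition of σ repeated, and the limits for plots are exp(μ ± σ).

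The statistic is specified in two places:

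- **Plasma concentrations.** The list of descriptive statistics includes "geometric coefficient of variance (%) (gCV"). Under Handling of Non-Quantifiable Concentrations, where more than half but not all values at a time point are non-quantifiable, "the gmean and gCV% are set to Not calculable (NC"), so no gCV is reported there.
- **PK parameters.** For Cmax, Cmin, Clast and the AUCs, the section on PK parameter descriptive statistics asks for "arithmetic mean of non log-transformed data (mean), arithmetic standard deviation (Std Dev), gCV(%), median, min and max", alongside n and the geometric mean. It also asks for gCV for dose-normalised exposures, λz, parameter ratios and the diagnostic parameters, but not for half-life, CL, Vss or MRT.

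Neither document gives another gCV formula; SAP Appendix B, which defines the PK parameters, has none.

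**The concern.** The formula and the definition of its symbol do not fit together. The CV of a log-normal variable depends on the log-scale variance, whereas the SAP puts the log-scale SD in that position.

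Reading σ as a variance would rescue the line, but the SAP excludes that reading. It calls σ a standard deviation twice and uses it in exp(σ) and exp(μ ± σ), both of which are right only for an SD.

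PK is a secondary objective, and gCV is the relative-variability figure that readers will take from the exposure tables. Programmed as written, the tables would show a between-participant spread inconsistent with the gSD plotted from the same data. Because the error changes direction at σ = 1, no fixed correction factor would repair published values.

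**Working it through.** **Inputs**

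- Printed formula: 100 × sqrt(exp(σ) − 1), from SAP 4.2.12.
- σ: the SD on the natural-log scale, from the same section.
- Value of σ: not given in either document. A range of 0.1 to 1.5 is assumed for illustration.

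The SAP states no numerical gCV, so there is no figure to reproduce; the check is of the formula.

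**Step 1: the log-normal CV.** If ln X is normal with mean μ and SD σ, then

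- mean of X = exp(μ + σ²/2)
- variance of X = exp(2μ + σ²) × (exp(σ²) − 1)
- CV = sqrt(variance)/mean = sqrt(exp(σ²) − 1)

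Hence gCV(%) = 100 × sqrt(exp(σ²) − 1).

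**Step 2: where the two forms agree.** They are equal only if σ = σ², that is at σ = 0 or σ = 1. For 0 < σ < 1, σ exceeds σ² and the printed form is too high; for σ > 1 it is too low.

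**Step 3: size.** At σ = 0.3, the printed form gives 100 × sqrt(exp(0.3) − 1) = 59.1% and the correct form gives 100 × sqrt(exp(0.09) − 1) = 30.7%. The last column is the SD/mean of 4,000,000 simulated log-normal values at each σ.

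| σ (assumed) | As printed (%) | Correct (%) | Printed/correct | Simulated CV (%) |
|---|---|---|---|---|
| 0.1 | 32.4 | 10.0 | 3.23 | 10.0 |
| 0.2 | 47.1 | 20.2 | 2.33 | 20.2 |
| 0.3 | 59.1 | 30.7 | 1.93 | 30.7 |
| 0.5 | 80.5 | 53.3 | 1.51 | 53.3 |
| 0.7 | 100.7 | 79.5 | 1.27 | 79.7 |
| 1.0 | 131.1 | 131.1 | 1.00 | 131.4 |
| 1.2 | 152.3 | 179.5 | 0.85 | 178.9 |
| 1.5 | 186.6 | 291.3 | 0.64 | 289.4 |

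The simulation follows the squared form throughout.

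**Step 4: the reverse direction.** Setting σ = sqrt(ln(1 + gCV²)), with gCV as a fraction, a true gCV of 20% would be printed as 46.8%, 30% as 58.4%, 50% as 77.7% and 100% as 114.0%.

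**Step 5: consistency with the SAP's own gSD.** At σ = 0.3, gSD = exp(0.3) = 1.35. Working back, ln(1.35) is 0.3 to two decimals, which corresponds to a gCV of 30.7%. The table beside the plot would show 59.1%.

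**Step 6: the alternative reading.** If σ were the log-scale variance, 0.09 would give 30.7% and 0.25 would give 53.3% from the printed formula, both correct. But exp(σ) would then no longer be the geometric SD, so this reading mends one line and breaks the next two.

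**The case against.** The algebra is not open to dispute. The strongest objection is that the SAP may be right and the machine-read text wrong. Only a superscript 2 is missing, and small characters were lost elsewhere in this section: the half-life symbol lacks its 2 under PK parameter descriptive statistics but has it in the rounding rules and in Table 14. The correct gSD lines next to the formula also fit an author who knew the right expression. Against this, the displayed formulas for BMI (SAP 4.1.5.1) and QTcF (SAP 4.2.1.7.1) kept their exponents, and the gCV line is a displayed formula of the same kind, whereas the half-life loss is in running text. A lost exponent is therefore possible but not shown. This part of the objection stands as a condition.

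A second objection is that reported values go wrong only if the formula is coded as printed; a standard software routine could give correct output from a misprinted SAP. Neither document shows the programs, so this stands too.

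A third is that little hangs on it. Wherever gCV is specified, the arithmetic mean, SD, median, minimum and maximum are specified as well, and individual PK parameters are listed, so readers keep valid measures of spread. gSD is called for only where plots need it, so the visible conflict may be limited. That is fair and bounds the consequence, but it does not make the formula right.

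Finally, the threefold overstatement applies only at an assumed σ of 0.1; at 0.7 the ratio is 1.27. The documents favour no part of the range.

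**Conclusion.** As printed, the gCV formula is wrong for the SAP's own definition of σ, except at σ = 0 or 1. Over the assumed range of log-SD from 0.1 to 1.5, the printed value runs from 3.23 times the correct one down to 0.64 times. The existence of the error does not depend on the assumed σ; only its size does.

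The consequence is limited to one descriptive PK column. The geometric mean, gSD, plot limits, and safety and efficacy analyses are unaffected.

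The conclusion rests on two conditions: that the source PDF shows the same formula as the text reviewed, and, for wrong values to reach the CSR, that the tables are programmed as written. Confidence is medium because of the first. It should be corrected, since it is a stated rule for reporting a secondary endpoint.

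**What to change.** 1. Check the gCV formula in the source SAP file. If σ is already squared, no change is needed.
2. If not, replace the line with gCV(%) = 100 × sqrt(exp(σ²) − 1). Keep σ as the log-scale SD and leave exp(σ) and exp(μ ± σ) as they are. Do not redefine σ as a variance.
3. Confirm that the PK concentration and parameter table programs use the squared form. A quick test is that log-data with an SD of 0.3 should return 30.7%, not 59.1%.

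The cost is one character in the SAP, plus a look at the source file and the table programs. No data collection or other analysis changes.

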### **Handling of Non-Quantifiable Concentrations**

Individual concentrations below the LLOQ of the bioanalytical assay are reported as NQ in the listings with the LLOQ defined in the footnotes of the relevant TFLs. Individual plasma concentrations that are Not Reportable are reported as NR and those that are missing are reported as NS (No Sample) in the listings. Plasma concentrations that are NQ, NR or NS are handled as follows for the provision of descriptive statistics:

- Any values reported as NR or NS are excluded from the summary tables and corresponding figures.
- At a time point where less than or equal to 50% of the concentration values are NQ, all NQ values are set to the LLOQ, and all descriptive statistics are calculated accordingly.
- At a time point where more than 50% (but not all) of the values are NQ, the gmean and gCV% are set to Not calculable (NC). The maximum value is reported from the individual data, and the minimum and median are set to NQ.
- If all concentrations are NQ at a time point, no descriptive statistics are calculated for that time point. The gmean, minimum, median and maximum are reported as NQ and the gCV% as NC.
- The number of values below LLOQ ( $n < \text{LLOQ}$ ) are reported for each time point together with the total number of collected values ( $n$ ).

Three observations  $>$  LLOQ are required as a minimum for a plasma concentration or PK parameter (e.g. Cmax, Cmin, Clast) to be summarised. Two observations  $>$  LLOQ are presented as minimum and maximum with the other summary statistics as NC.

### **PK parameter Listings**

All reportable PK parameters, including individual diagnostic and lambda z related parameters, are listed for each participant by Study Part, PK Day/Visit and Treatment, for each analyte separately.

### **PK parameter descriptive statistics**

All primary and secondary PK parameters are summarised for each analyte by Study Part, PK Day/Visit and Treatment dose using appropriate descriptive statistics. Similar parameter data (e.g., single dose or multiple doses for the same dosing regimen) from different Study Parts or PK Days/Visits may also be summarised together.

The descriptive statistics for PK parameters are presented as follows:

- Cmax, Cmin, Clast, AUC(0-t), AUCinf, AUClτ, AUClast: present n, gmean, arithmetic mean of non log-transformed data (mean), arithmetic standard deviation (Std Dev), gCV(%), median, min and max.
- $t^{1/\lambda z}$ , CL, Vss, MRT, : present n, arithmetic mean of non log-transformed data (mean), arithmetic standard deviation (Std Dev), median, min and max.
- Cmax/D, AUCinf/D, AUC(0-t)/D, AUClτ/D, AUClast/D,  $\lambda z$ , and all parameter ratios (e.g Rac, TCP, peak:trough ratio and fed to fasted ratios): present n, gmean, gCV(%), mean, Std Dev, median, min and max.
- tmax, tlag, and tlast: present n, median, min and max.
- Diagnostic parameters (e.g. t upper, t lower, n obs, Rsq adj and AUCextr): present n, arithmetic mean, Std Dev, gmean, gCV%, median, min and max.

Three values are required as a minimum for PK parameters to be summarised. Two values are presented as a min and max with the other summary statistics as NC.

If one or more values for a given parameter is zero, then no geometric statistics are calculated for that parameter and the results for geometric statistics are set to NA (Not Applicable).

### **Graphical presentation of PK data**

All mean (arithmetic mean and/or gmean) plots or combined plots showing all participants by treatment are based on the PK analysis set. Individual plots by participant are based on the safety analysis set. Scatter plots for individual PK parameters versus Treatment dose present both summary parameter data and individual participant parameter data for each Treatment dose including only participants in the PK analysis set.

For consistency, the plasma concentration values used in the mean (arithmetic mean and/or gmean) data graphs are those given in the descriptive statistics summary table for each time point.

For gmean concentration-time plots, NQ values are handled as described for the descriptive statistics; if the geometric mean is NQ, the value plotted is zero for linear plots and missing for semi-logarithmic plots. Any gmean $\pm$ gSD error bar values that are negative are truncated at zero on linear concentration-time plots and omitted from semi-logarithmic plots.

For individual plots, plasma concentrations which are NQ prior to the first quantifiable concentration are set to a value of zero (linear plots only). After the first quantifiable concentration, any NQ plasma concentrations are regarded as missing.

Data permitting, the following figures are presented as appropriate:

- Figures for the mean (arithmetic mean and/or gmean) plasma concentration-time data (with  $\pm$ Std Dev and/or  $\pm$ gSD error bars) presented on both linear and semi-logarithmic scales using scheduled post-dose time as follows:
  - By PK Day for each analyte with all or selected single dose Treatments (e.g., dose level) overlaid on the same plot and/or all or selected multiple dose Treatments (e.g., dose levels and schedule) overlaid on the same plot
  - By PK Treatment for each analyte with all or selected single dose PK days and all or selected multiple doses PK Days overlaid on the same plot
  - By PK Treatment with all or selected single dose PK days for each analyte overlaid on the same plot and/or all or selected multiple doses PK Days for each analyte overlaid on the same plot
- Individual participant plasma concentration-time data graphically presented on both linear and semi-logarithmic scales using actual time post-dose as:
  - By participant with all and/or selected PK Days for the same participant overlaid on the same plot
  - Combined individual plots with all participants overlaid on the same plot for each single dose Treatment (e.g., dose level) and/or each multiple dose Treatment (e.g., dose level and schedule)
- Individual and summary single dose and/or multiple dose PK parameter data graphically presented on scatter plots of the PK parameter value
- Individual and summary single dose and/or multiple dose PK parameter data graphically presented as line plots of the PK parameter value against treatment with each individual and the mean value joined with a line between the treatment

- Ratios of a single dose and/or multiple dose PK parameter value for one Treatment (e.g., in combination with another drug or under fed conditions) divided by the value for another Treatment (e.g., not in combination with the other drug or under fasted conditions respectively) plotted against each individual participant or against each Treatment
- Scatter plot of pharmacokinetic parameters (Cmax, AUCinf and AUC(0-t)) versus dose presented on logarithmic scales

## Precision and Rounding Rules for Pharmacokinetic Data

### PK concentration data

PK concentration data listings present to the same number of significant figures as the data received from the bioanalytical laboratory (usually but not always to 3 significant figures) and against the same units as received.

PK concentration descriptive statistics present 4 significant figures with the exception of the min and max which present 3 significant figures and n and n<LLOQ which present as integers.

### PK parameter data

PK parameter listings are presented according to the following rules:

- Cmax, Cmin and Clast: present to the same number of significant figures as received from the bioanalytical laboratory
- tmax, tlast, tlag, t lower and t upper: present as received in the data, usually to 2 decimal places
- AUCinf, AUC(0-t), AUC $\tau$ , AUClast, AUC/D, AUC(0-t)/D, AUC $\tau$ /D, AUClast/D, AUCextr,  $\lambda_z$ ,  $t^{1/2}\lambda_z$ , CL,MRT, Vss, Vz, all ratios of PK parameters (e.g. Rac, TCP, Peak:Trough ratio), Rsq adj, : present to 3 significant figures
- F and Frel: present to 2 decimal places
- n obs: present as an integer (no decimals)

The descriptive statistics for PK parameter data are presented to 4 significant figures with the exception of the min and max which are presented to 3 significant figures apart from the following:

- $\lambda_z$ : present to 5 significant figures with min and max to 3 significant figures

- $t_{max}$ ,  $t_{lag}$ , and  $t_{last}$ : present as received in the data, usually to 2 decimal places
- number of values (n): present as an integer

